#### 8 SUBJECT CONFIDENTIALITY

Subject confidentiality is held strictly in trust by the participating investigators, their staff, the sponsor, and their agents. The study protocol, documentation, data, and all other information generated will be held in strict confidence. No information concerning the study, or the data will be released to any unauthorized third party without prior written approval of the sponsor. The clinical study site will permit access to appropriate documents and records that may require inspection by the sponsor or its authorized representatives including de-identified study data.

Only IRB-registered protocol staff will have access to the actual identities of the participants, which will remain anonymous to all non-IRB authorized persons.

The sources of human research data will include the following.

- 1. Demographic information, including age, sex, race, and ethnicity.
- 2. Results of screening instruments.
- 3. Rater-blinded assessment instruments including: JTHFT, QUEST, and WMFT.
- 4. Parental report instrument Pediatric Motor Activity Log.
- 5. MOVE-IT game-derived measures including achieved therapy duration, and functional movement repetitions.
- 6. Weekly activity logs
- 7. SUS and TAM usability questionnaires
- 8. Transcribed usability data including think-aloud expressions during system use; captured in digital video, screen captures, and therapist notes.

Potential risks of accidental release of identifying and/or confidential information will be mitigated by use of a de-identified coded key for all subject data. The cipher that relates participants to the key will exist in hard (paper) copy only and be stored in a locked cabinet in a controlled-access room at the study sites. All data sheets will be properly controlled and shredded prior to disposal.

De-identified data covering primary and secondary measures will be analyzed by the study biostatistician. The de-identified data and the results of biostatistical analysis will be provided to the sponsor via encrypted means. Results will be reported by the sponsor to the NIH via annual and final progress reports, and incorporated into one or more manuscripts to be submitted for publication in

medical journals and/or conference proceedings accessible via PubMed Central. ClinicalTrials.gov and results information will be submitted according to ClinicalTrials.gov	RCT will	be register	ed with

#### 9 INFORMED CONSENT

The informed consent process includes parental or legal guardian permission and child verbal assent. All permission and assent forms will be approved by the IRB. Initial prescreening will be conducted by telephone to determine if a candidate meets basic enrollment criteria including age, diagnosis, and general health status. The parent or guardian of individuals passing phone prescreening will be provided a read-ahead copy of the permission and assent forms. The forms will include a summary of the study protocols, details on inclusion and exclusion criteria, and details on exercise components. Candidates will subsequently be scheduled for an initial consent and screening visit.

During the administration of the permission and assent process, trained study staff will provide the parent or guardian and child an informational overview, verbally guide them through the permission form, provide a summary for each section and ask for verbal confirmation of understanding of each section. The parent will then be given an opportunity to read the entire form, or have the form read to them if they are unable or prefer not to read it themselves. The study therapist will then verify understanding by asking the following question: "If you were to explain what is happening in this study to a family member or friend, what would you say to them?" If the parent or guardian is unable to demonstrate understanding, the study therapist will re-review the permission form and repeat the question. Individuals will be informed of the ability to withdraw from the study at any time and for any reason with no negative consequence.

If the parent or guardian demonstrates understanding of the protocol, he/she will be given the opportunity to sign the permission form. The child will then be given the opportunity to provide assent. The child will be provided with a summary of the study and give the opportunity to demonstrate his or her understanding and willingness to participate. If permission and assent are provided, the parent or guardian will be provided a copy of the signed forms. The original will be filed in the secure study file.

#### Consent Visit (in-person or remotely administered, will last about 45 minutes)

- The child and a parent/guardian will take part in remotely-administered telehealth visit with a study coordinator or a study therapist by phone or HIPAA compliant video conferencing (e.g. Zoom Health) OR take part in-person.
- Participants will be asked pre-screening questions to verify inclusion and exclusion criteria.
- Participants at the University of Virginia will complete informed consent and assent using DocuSign or alternative institutionally-approved method.

-	Participants at Duke University will complete informed consent and assent using a wet signature if the consenting meetings takes place in-person, such as in clinic. If the consenting process takes place via HIPAA compliant video conferencing or phone, study staff will direct the parent/guardian to sign the consent in the appropriate spaces. Study staff will then provide a mailing address for the participant to send the completed consent form. Duke study staff will document the reason remote consent was obtained (i.e. in-person consent not possible due to distance from Duke University).

# 10 DATA AND SAFETY MONITORING PLAN-IRB-HSR TO SERVE AS SIRB OF RECORD

This study has been deemed minimal risk. Because this study poses minimal risk to the subject, adverse events will only be collected or recorded if a causal relationship to the study intervention is suspected. If any adverse event is considered serious and unexpected, the event must be reported to the IRB-HSR within 7 days from the time the study team receives knowledge of the event.

#### 10.1 Definitions

#### 10.1.1 How will you define adverse events (AE)?

Do not change this answer

An adverse event will be considered any undesirable sign, symptom or medical condition considered **related to the intervention**. Medical condition/diseases present before starting the intervention will be considered adverse events only if they worsen after starting the study and that worsening is considered to be related to the study intervention. An adverse event is also any undesirable and unintended effect of research occurring in human subjects as a result of the collection of identifiable private information under the research.

#### 10.1.2 How will you define an unanticipated problem?

Do not change this answer

An unanticipated problem is any issue that involves increased risk(s)

to participants or others. This means issues or problems that cause the subject or others to be placed at greater risk than previously identified, even if the subject or others do not incur actual harm. For example if a subject's

confidentiality is compromised resulting in serious negative social, legal or economic ramifications, an unanticipated problem would need to be reported. (e.g. serious loss of social status, loss of job, interpersonal conflict.)

#### 10.1.3 What are the definitions of a protocol deviation and/or noncompliance?

Do not change this answer

A protocol deviation is defined as any change, deviation, or departure from the study design or procedures of research project that is NOT approved by the IRB-HSR prior to its initiation or implementation. Protocol deviations may be major or minor.

**Noncompliance can be a protocol deviation OR deviation from** standard operating procedures, Good Clinical Practices (GCPs), federal, state or local regulations. Noncompliance may be minor or sporadic, or it may be serious or continuing.

Additional Information: see the IRB-HSR website at

Protocol Deviations, Non-compliance and Protocol Exceptions

#### 10.2 What risks are expected due to the intervention in this protocol?

Expected Risks related to study participation	Pick One
There is a small risk that breaches of privacy and/or	Occurs rarely
confidentiality might occur. The risk of violation of subject	
privacy and confidentiality is minimal due to the requirements	
of the privacy plan in this protocol.	
There is a minor risk that soreness, pain, or increased tone	Occurs rarely
may occur post-use due to increased range and level of	
activity involving the upper extremity. The risk is minor as	
game-integrated movements are consistent with accepted	

clinical practice and exercises used in previous RCTs involving	
similar therapy (e.g. the CHAMP R01 RCT, [12]).	
There is a minor risk of elevated stress or embarrassment due	Occurs rarely
to frustration with the interface or inability to perform a task.	
The risk is minor as cognitive demands are progressive and	
appropriate for the participant population and consistent with	
existing clinical practice. Study pediatric therapists will tailor	
the activities to the capabilities of the patient.	

10.3 When will recording and	reporting of unanticipated	problems/adverse events begin?
------------------------------	----------------------------	--------------------------------

\_\_x\_\_\_After subject begins study intervention

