#### 4 STUDY DESIGN

The study is a randomized control study.

Following screening, enrolled subjects will be randomized to either the MOVE-IT home exercise program (HEP) or usual care treatment (UCT) group using a centralized and masked process developed by the study biostatistician. The HEP group is the interventional group. The UCT group is the control group. Following the control strategy previously adopted in the Children with Hemiparesis Arm and Movement Project (CHAMP) multi-site RCT (NICHD R01, trial registration number NCT01895660), children in the UCT group will be followed as they continue to receive their previously prescribed therapy services. As UCT group participants, these children will not receive any treatment services through the study. Parents will be asked to report therapy services their children receive during each assessment visit.

To ensure that an approximately equal number of subjects are randomized to the MOVE-IT HEP and UCT groups throughout the Phase II enrollment period, we will randomly assign the patients to the two study-groups in accordance with a permuted block randomization scheme. The randomization list will be generated by a UVA study biostatistician ([name]) using the PLAN procedure of SAS (SAS Institute Inc., Cary, NC). One subject randomization table will be generated for each site. The group assignment will be blinded to the therapists (raters) who perform the pre- and post-assessments. The group assignment will be not be blinded to the participants. The non-rater members of the IRB-approved study team will have access to the randomization list.

Demonstration of statistically significant improvement in UE motor function for participants the MOVE-IT HEP versus UCT will support the validity of MOVE-IT use as an intervention for children with hemiplegia. In home use, MOVE-IT will enable more frequent and intensive therapy with reduced travel and may extend the service range of existing rehabilitation providers to include underserved areas. In clinical practice, MOVE-IT will enable new models of delivery based on remote monitoring combined with outpatient services, increasing quality and efficiency of care. Statistical considerations for sample size determination, primary analysis, and secondary analyses are described below.

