#### **GROUP 2: UCT GROUP:**

- Participants in the control group will continue to receive any previously prescribed therapy services. These patients will not receive any treatment services through the study as UCT group participants.
- At least once every two weeks during the interventional period, non-blinded study staff will contact the participant by phone or HIPAA compliant video conferencing to collect self-reported adherence data and confirm that no change in medical status has occurred that would impact continued participation.

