# 10.4 When will the recording/reporting of unanticipated problems/adverse events end?

\_\_\_x\_Subject completes participation in the protocol

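### Safety recording under 10.3 starts after consent and baseline testing and has no defined start for usual-care children; the relatedness filter also rules out comparing expected symptoms between arms

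*Combined protocol and SAP*

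**What the plan says.** Four parts of the protocol bear on this.

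- **Window.** Section 10.3 ticks one option for the start of recording and reporting of both unanticipated problems and adverse events: "After subject begins study intervention". Section 10.4 ends it when "Subject completes participation in the protocol".
- **Filter.** The opening of section 10 calls the study minimal risk and, on that ground, says that "adverse events will only be collected or recorded if a causal relationship to the study intervention is suspected". Section 10.1.1 matches it: an adverse event is "any undesirable sign, symptom or medical condition considered" related to the intervention. That definition has a second limb, for unintended effects on subjects "as a result of the collection of identifiable private information under the research". Section 10.1.2 defines an unanticipated problem by increased risk to participants or others, and requires no link to the intervention or to an arm.
- **Arms.** Section 4 states: "The HEP group is the interventional group". Section 6.1 says of the controls: "These patients will not receive any treatment services through the study as UCT group participants".
- **Contacts.** Section 6.1 plans a contact at least every two weeks in each arm to check medical status. Section 2.3.1 says that at such contacts staff ask about soreness, pain and increased tone and take concerns to the PI. It also provides for reported stress or frustration.

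**The concern.** The recording window is tied to an event that only one arm clearly has, while some of the risks that the protocol lists exist in both arms and begin at consent. Section 10.2 lists loss of privacy as a risk of taking part, and that risk starts when the first identifiable data are collected.

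The relatedness filter has a separate effect. Soreness, pain and altered tone can occur in children with hemiplegia under any care. If they are recorded only where MOVE-IT is suspected as the cause, there is no concurrent background rate. The trial could then list symptoms attributed to the device, but could not say whether they are more frequent than under usual care.

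**Working it through.** The protocol states no event rate or safety sample size, so there is no figure to reproduce. The check sets the passages side by side.

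**1. Order of events.** The consent visit (section 9, about 45 minutes) comes first. Outpatient Visit 1 follows (section 6.1, about 90 minutes, with JTHFT, QUEST and WMFT), and assignment to an arm is its last step. The intervention can begin only after that. Consent and baseline testing therefore precede the 10.3 start for all 48 dyads.

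**2. Start for UCT.** Section 7.2 plans 24 children per group, so 24/48 = 50% are UCT. They receive nothing through the study. Access to MOVE-IT is offered only after the control protocol is complete, so it supplies no start during the controlled period. Section 6.1 does place the UCT contacts within the interventional period, and section 7.3 speaks of an interventional or control period, but no passage says that this period opens the 10.3 window for a UCT child. The start is undefined.

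**3. Definitions against window.**

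| Type of event | Link to intervention required? | Effect of 10.3 |
|---|---|---|
| Clinical adverse event (10, 10.1.1) | Yes | Not captured at baseline or in UCT |
| Privacy-related adverse event (10.1.1, second limb) | No | Delayed past consent and baseline; start undefined in UCT |
| Unanticipated problem (10.1.2) | No | Same |
| Data breach or deviation (10.6) | No | None; own reporting rows, not tied to 10.3 or to an arm |

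Rows two and three are the conflict: 10.1 includes the event, but 10.3 delays its recording or leaves the start open.

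**4. Comparison between arms.** Suppose the shared calendar period is read as giving UCT children a start. The filter still removes their clinical events, because they have no study intervention to which an event could be related. The comparison is lost on either reading.

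**5. What a symptom record in UCT would add.** As an illustration, suppose a symptom is reported by none of n children. The exact two-sided 95% upper limit is 1 − 0.025^(1/n):

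- n = 24 (all enrolled): 1 − 0.025^(1/24) = 14.2%
- n = 20 (planned completers, section 7.2): 1 − 0.025^(1/20) = 16.8%

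The one-sided limits, 1 − 0.05^(1/n), are 11.7% and 13.9%. These bounds are for a single arm. They show that the record would be coarse; they do not measure the power of a comparison.

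**6. Workload.** One contact every two weeks over 10 weeks gives 10/2 = 5 per child. For 48 children that is 5 × 48 = 240 short entries at the minimum frequency, if all are followed.

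**The case against.** The best defence is that the filter is a reasoned choice. The study is classed as minimal risk, the definition in 10.1.1 carries a label saying that it must not be changed, and between-arm safety is neither an objective (section 3) nor a planned analysis (section 7.4). Staff already ask about the main symptoms (section 2.3.1), and UCT families are contacted as often as HEP families. All of this stands as a reason to keep the filter for IRB reporting. It does not settle the conflict between 10.3 and 10.1. Nor does any passage say that answers given at the contacts are recorded as safety data, or that UCT families are asked the symptom questions: section 2.3.1 is written about the risks of using MOVE-IT.

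A reader might infer more than the documents support:

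- *That the whole UCT arm is outside safety oversight.* The medical-status contacts and the 10.6 reporting rows apply to UCT, and 10.1.1 and 10.1.2 reach beyond the intervention.
- *That privacy breaches in half of the children would go unrecorded.* Data breaches have their own reporting route: within 24 hours at UVA, and under local rules at the other site. Section 10.5 also places them under aggregate review.
- *That recording never starts in UCT.* The wording on the shared period leaves this open.
- *That unblinded staff judge relatedness.* They make the contacts, but no passage assigns that judgement, and section 2.3.1 sends concerns to the PI.

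**Conclusion.** The concern holds in a limited form. For all 48 dyads, consent and baseline testing fall before the stated start. For the 24 planned UCT children (50%), no start is defined. Both conflict with the scope of 10.1.1 and 10.1.2. Separately, and on any reading of the start, clinical events in UCT children do not enter the adverse event record, so the 10.2 symptoms have no concurrent reference rate.

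This rests on the current text and on planned rather than achieved group sizes. It does not touch the primary efficacy analysis. It is worth correcting because the text has to be reconciled in any case and the contacts that would supply the missing data are already planned.

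**What to change.** 1. In 10.3, start recording of unanticipated problems and adverse events at consent, in both arms. This option carries no label against change, unlike 10.1 and 10.5.
2. In section 6.1, put the same symptom questions (soreness, pain, increased tone, stress) in the same words at the two-weekly contacts in both arms. Record the answers as solicited symptoms whatever the suspected cause.
3. In section 7.4, add a descriptive table of these symptoms by arm.
4. Leave the 10.1.1 definition and the relatedness filter in place for IRB reporting. Add a line to the opening of section 10 so that its limit on collection does not bar the symptom record.

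The cost is a protocol amendment, a few lines on the contact form and more minor events to log (about 240 short entries at the minimum frequency). No new contacts or staff are needed.

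Two limits remain. Under the retained definition, a minor clinical event during baseline testing would still not count as an adverse event unless it amounted to an unanticipated problem. Families also know their assignment (section 4), so the symptom table is open to reporting bias and should be read as descriptive.

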# 10.4 When will the recording/reporting of unanticipated problems/adverse events end?

\_\_\_x\_Subject completes participation in the protocol

# 10.5 What is your plan for safety monitoring?

Do not change this answer

Safety monitoring and aggregate review of adverse events, unanticipated problems, protocol violations and any data breach will be performed by the PI and IRB-HSR through continuation review at least annually.

# 10.6 What is your plan for reporting an Unanticipated Problem, Protocol Deviations or Data Breach?

# 10.6.1 Reporting Requirements for UVA Site

Type of Event	To whom will it be reported:	Time Frame for Reporting	How reported?
Unanticipated Problems that are not adverse events or protocol deviations This might include a Data Breach.	IRB-HSR	Within 7 calendar days from the time the study team received knowledge of the event.	Unanticipated Problem Report Form  Unanticipated Problem Report Form
Protocol Deviations/Noncompliance (The IRB-HSR only requires that MAJOR deviations be reported, unless otherwise required by your sponsor, if applicable.)		Within 7 calendar days from the time the study team received knowledge of the event.	Protocol Deviation, Noncompliance and Protocol Exception Reporting Form  Protocol Deviation Protocol Exception Reporting Form

Data Breach* of Protected	The UVa Corporate	As soon as possible	UVa Corporate Compliance and Privacy Office- [contact]
Health Information	Compliance and	and no later than 24	
	Privacy Office	hours from the time the incident is	
		identified.	
	ITC: if breach	identified.	ITC: Information Security Incident Reporting procedure,
	involves electronic	As soon as possible	https://security.virginia.edu/report-information-security-incident
	data	and no later than 24	
		hours from the time	
		the incident is	
		identified.	
	Police if breach		
	includes items that	IMMEDIATELY.	Police: phone- [contact]
	are stolen:		
	Stolen on UVA		
	Grounds		
	OR		
	Stolen off UVa		
	Grounds- contact		
	police department of		
	jurisdiction of last		
	known location of		
	PHI		

\*A data breach is defined in the HITECH Act (43 USC 17932) as an unauthorized acquisition, access, or use of protected health information (PHI) that compromises the security or privacy of such information.

Additional Information may be found on the IRB-HSR Website: Data Breach

# 10.6.2 Reporting Requirements for the non-UVA site(s)

Type of Event	To whom will it be reported:	Time Frame for Reporting	How reported?
Unanticipated Problems that are not	UVA study team/ Data	Within 7 calendar	Written documentation.
adverse events or protocol deviations	Coordinating Center	days from the	
This might include a Data Breach.		time the study	May use the Relying Site Unanticipated Problem Reporting
	UVA lead site or DCC	team received	Form
	will report to the IRB- HSR per table above	knowledge of the event.	
Protocol Deviations/Noncompliance	UVA study team/ Data	Within 7 calendar	
The IRB-HSR only requires that MAJOR	Coordinating Center	days from the	Written documentation.
deviations be reported, unless otherwise		time the study	
required by your sponsor, if applicable.	UVA lead site or DCC	team received	May use the Relying Site Protocol Deviation/Exception
	will report to the IRB-	knowledge of the	Reporting Form
OR	HSR per table above	event.	
Protocol Exceptions			
See definition- only allowed if there is a			
commercial sponsor or a DSMB that has			
granted the protocol exception.			

Data Breach	Per local relying	Per local relying	Per local relying institution requirements.
	institution	institution	
	requirements	requirements	
	The UVA IRB-HSR only		
	needs to be notified of		
	any data breach that		
	meets the criteria of a		
	UP		

